# The Intervention

The intervention to be delivered as part of this study is informed by previous research by the team (MRC PHIND MR/S002286/1). Realist review methods, stakeholder consultation and built on the MRC guidance for developing complex interventions, was used to develop the *Handbook* 

for Nature-on-Prescription (Fullam et al, 2021). In the handbook, we detail key active mechanisms, common to many types of nature-based activities, though which benefits may come about. The handbook details strategies to optimise delivery of nature-based interventions through incorporation of activities that activate these pathways. Key mechanisms are:

- Group-based participation. When positive and meaningful psychological
  connections are established between group members, the content of health
  interventions may be enhanced (Tarrant et al, 2016). Groups can reduce loneliness
  (a common reason for SP referrals), build self-esteem, reduce worry and rumination
  and reduce a sense of despair and hopelessness.
- Caring for things. People can find solace, and develop self-esteem, in caring for plants, nature, and/or animals and develop a sense of reciprocal benefit between themselves and nature (Sempik et al, 2010). They may also care for others in the group and for themselves through this process.
- Having fun and enjoyment, is an important component of wellbeing, helping to contribute to a worthwhile and satisfied life (Haworth, 2016). It is also linked to completion and adherence with health-related interventions (Herens et al, 2016).
- Personal growth. While this may be through formal therapeutic approaches, such as CBT, or meditation skills, such as mindfulness, even without formal approaches, participants can develop knowledge or skills and experience a range of achievements.
- Making a difference. Some forms of nature-based activities involve tangible, and potentially appreciated, contributions to the community (e.g. through improving the environment) This can contribute to mental health, social function, and wellbeing (Lovell et al, 2015).
- Creating. Active processes of 'making' may benefit wellbeing (Thomlinson et al 2018). Nature-based creative activities, including gardening, have been linked to mental health through refuge from stress, and self-development (Genter, 2015).
- Physical activity. Exercise and physical activity have been shown to support physical and mental health (Cooney et al, 2013; Penedo et al, 2005) and exercise in outdoor natural environments is more beneficial, in terms of self-reported mental wellbeing, than that taking place indoors (Thompson Coon et al, 2011).
- Being outside. Participants in nature-based interventions describe the outdoor environments as simple, peaceful, and, crucially, 'away' or 'other' to their usual environment, offering fresh air, a change of scene and a sense of space (Burls et al, 2007; Maund et al, 2019).
- Developing a relationship with nature. This mechanism may operate through counteracting stress and increasing the ability to focus and concentrate (supporting Attention Restoration Theory (Ohly et al, 2016)). People may also develop a symbolic association with natural cycles of dormancy and growth, regeneration and regrowth, which they find helpful in understanding their own condition (Garside et al, 2021).

The programme of nature-based activities delivered by each partner organisation will be mapped to these intervention mechanisms to ensure anticipated delivery fidelity. It is expected that all sessions will involve two key mechanisms – being outside and being in a group. In addition, over the course of the programme, the activities will involve at least 80% of the

mechanisms. Researchers will attend at least one session per provider to observe and log how the activities are carried out in practice (fidelity). In addition, all participants will be asked to attend an intervention site induction visit prior to the start of the intervention so that they know how to get there, be introduced to course leaders and orientate themselves in the site and its activities. If participants do not have appropriate waterproof clothing and footwear, this will be provided by the site.

Staff will be experienced in delivering nature-based activities and will have experience and/or training in mental health first aid. In addition, participating organisations have appropriate safeguarding, risk assessment, insurance, data management systems (GDPR compliant) policies as a prerequisite to being a study partner. Nature-based activity providers will be required to log any adverse events such as injuries during the delivered course.

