# Role of Trial Sponsor and Funder

Ther University of Exeter is the sponsor of this study. The study sponsor will ensure that the research team has access to resources and support to deliver the research as proposed and that responsibilities for management, monitoring and reporting of the research are in place prior to the study commencing. The sponsor will ensure that there is agreement on recording, reporting and reviewing significant developments as the research proceeds and approve any modifications to design, obtaining requisite regulatory authority approval. The sponsor will assume responsibility for operating the management and monitoring systems of the research.

Prior to the study commencing the sponsor will be satisfied that:

- The research will respect the dignity, rights, safety and well-being of participants and the relationship with healthcare professionals.
- Where appropriate the research has been reviewed and approved by an NHS Research Ethics Committee and/or the Health Research Authority Approval Programme.
- The Chief Investigator, and other key researchers have the requisite expertise and have access needed to conduct the research successfully.
- The arrangements and resources proposed for the research will allow the collection of high quality, accurate data and the systems and resources will allow appropriate data analysis and data protection.
- Organisations and individuals involved in the research agree the division of responsibilities between them.
- Arrangements are in place for the sponsor and other stakeholder organisations to be alerted to significant developments during the study, whether in relation to the safety of individuals or scientific direction.
- There are arrangements for the conclusion of the study including appropriate plans for the dissemination of findings.

The sponsor plays no role in the design of this study and will have no role in data analysis or interpretation or writing up of findings of the study.

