# Roles and Responsibilities of Trial Management Committees/Groups & Individuals

The trial management group meets monthly to ensure that the practical details of the trial are progressing well and that everyone in the team understands them. They provide expert advice about trial design and processes and will contribute to data analysis, interpretation and writing manuscripts.

The Trial Steering Committee (TSC) will be composed of an independent chairperson with expert knowledge in the subject area, an independent statistician, Patient and Public Involvement (PPI) representative(s) and at least one other independent professional member. The Chief Investigator and another member of the trial management group will join the TSC as non-independent members. Observers will be invited to attend TSC meetings but will not be voting members (e.g. trial manager, trial statistician, health economist).

The role of the TSC is to monitor and supervise the progress of the trial. The TSC will meet prior to recruitment commencing and approximately 6-monthly thereafter.

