# Ethical and regulatory considerations

Quantitative data collection will involve the participants answering questions about how they feel and their mental health, including anxiety and depression specific instruments. Sometimes reflection on the issues raised by the data collection tools can cause distress. Participants will be reminded that they don't have to complete the information if they don't want to, with no disbenefit to themselves. Details of local GP and MH services will be provided online with the questionnaires and in the information sheets.

In the focus groups, participants will be told they can take a break or stop taking part at any time. If people seem to be upset, the researcher moderating the focus group will check in with them, ask if they want to continue, and given the chance to leave the group. They will be followed up a researcher (all groups will have 2 moderators). Moderators will comfort them and reassure them if possible and will have a list of local numbers to supply to the participants if helpful.

In the event that there were concerns around the health or well-being of participants then these would be flagged by the providers, discussed with the participants and the PI contacted if necessary. It will be made clear in the Participant Information Sheet that the researcher has a duty to inform an individual's GP if, during the course of discussions, they become aware of any risk or harm to the participant themselves. Researchers would always discuss this with the participants before doing so, unless the urgency of need makes this impractical.

A list of local mental health support numbers and the Samaritans will be provided with the participant information sheets.

The study is subject to HRA Assessment to obtain ethical approval.

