# Assessment and management of risk

All activities will take place outdoors, there may be inclement weather, minor injuries related to walking, use of gardening equipment etc. The nature-based providers will log any adverse events and follow their existing policies and procedures for dealing with minor injuries.

Participants will be advised to bring any allergy medication they have with them (in case of, for example hay fever) and will be required to inform the group leader if they have any serious allergies, (for example to bee stings), or health conditions that may be affected by taking part in the activities.

Green partners are experienced practitioners and will abide by their own risk and safety policies during the intervention.

The study may involve the research fellows working on sites away from the University of Exeter. Prior to any visit they will inform the Chief Investigator of the location and schedule in accordance with the University of Exeter lone working policy. A dedicated project phone sim card will be acquired for the project.

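### Adverse events are recorded only by providers and only during courses, so none can be recorded in controls before T2 and the arms cannot be compared on them

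*Protocol*

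**What the plan says.** The protocol sets a recording rule for adverse events in two places. The Intervention says: "Nature-based activity providers will be required to log any adverse events such as injuries during the delivered course". Assessment and management of risk says: "The nature-based providers will log any adverse events and follow their existing policies and procedures for dealing with minor injuries". No other section names a recorder, a form or a time window for adverse events.

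Three other provisions bear on the point:

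- Under Ethical and regulatory considerations, concerns about a participant's health or wellbeing would be "flagged by the providers, discussed with the participants and the PI contacted if necessary".
- The same section says that "the researcher has a duty to inform an individual's GP if, during the course of discussions, they become aware of any risk or harm".
- Role of Trial Sponsor and Funder lists matters on which the sponsor will be satisfied before the start, among them: "Arrangements are in place for the sponsor and other stakeholder organisations to be alerted to significant developments during the study". That item expressly extends to the safety of individuals.

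Table 7 (Assessment Processes) lists the participant-reported instruments. It includes PHQ-9, GAD-7 and the healthcare use questionnaire at T0, T1 and T2, a participation survey at T1, and a withdrawal survey at any time after randomisation. It lists no adverse-event item. Trial Procedures and Control Arm both place the controls' offer of a course after T2.

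**The concern.** The recording rule ties adverse events to attendance at a course, and before T2 only one arm attends one. The asymmetry comes from how the data are gathered, so it cannot be repaired at the analysis stage.

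Some foreseeable harm is also unrelated to the course. Ethical and regulatory considerations accepts that answering the questionnaires may be distressing, and both arms answer them three times.

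What is at stake is mainly the next trial. This pilot exists to test and settle the processes of a definitive RCT. A one-armed adverse-event process would pass into that trial without a two-armed version having been tried.

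**Working it through.** **Step 1: the timeline.** Inputs are the expected 2-week gap from randomisation to course start (Data Flow and Qualitative Process Evaluation Data), the 6-week course, and a further 6 weeks to T2.

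- T1 = 2 + 6 = 8 weeks after randomisation.
- T2 = 8 + 6 = 14 weeks after randomisation.

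Both match the figures under Methods.

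**Step 2: place the recording rule on the timeline.** Planned size is 42 per arm (Trial Summary).

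| Weeks after randomisation | Intervention arm (42) | Control arm (42) |
|---|---|---|
| 0 to 2, before the course | no course running | no course running |
| 2 to 8, course | provider log | none |
| 8 to 14, T1 to T2 | none | none |
| after T2, wait-list course | not applicable | provider log, but comparison period over |

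Before T2 the intervention arm is covered for 6 of 14 weeks and uncovered for 2 + 6 = 8. The control arm is covered for 0 of 14. An induction visit is treated here as outside the delivered course. Even in covered weeks, the log holds only what a provider sees or is told.

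**Step 3: what both arms do supply.** PHQ-9, GAD-7 and health service use at T1 and T2 show symptom worsening and service contacts. The withdrawal survey shows reasons for leaving. Planned Data Analysis states adjusted mean differences with 95% confidence intervals for the mental health and wellbeing outcomes. A mean difference does not show how many individuals got worse, and no such count is stated.

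The scores allow one. Exclusion criteria define the severe range as PHQ-9 of 20 or more, or GAD-7 of 15 or more. Everyone enrolled was below both limits at screening, so anyone in that range at T1 or T2 has crossed a limit since then.

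**Step 4: where the log goes.** Attendance is the useful contrast. It has a prespecified collection tool (Data collection, entry, coding and checking processes) and appears in the trial's data flow. The adverse-event log has neither. The escalation route runs on health concerns and on a judgement of necessity. The sponsor-alert undertaking is general. Neither refers to the log.

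**The case against.** The strongest reply is that this is a low-risk outdoor programme in an 84-person pilot that excludes severe cases, that logging spans the whole period of exposure, and that no between-arm comparison of adverse events is proposed. All of that is true. The last part means that no planned table is biased. The point is narrower: the data for any such comparison will not exist. Summaries may be left to an analysis plan, but collection cannot.

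A reader might go further in four ways that the protocol does not support.

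- **That provider concerns cannot reach the trial team.** They can: the principal investigator is contacted if necessary, regular provider meetings run throughout, and researchers must inform the GP of risk or harm. What is missing is a link from these routes to the log.
- **That the log is kept under each provider's own policies.** "The nature-based providers will log any adverse events and follow their existing policies and procedures for dealing with minor injuries" applies those policies to dealing with minor injuries, not to custody of the log.
- **That worsening goes unseen.** Symptom scores, service use and withdrawal reasons are collected in both arms, and the free-text surveys may catch more.
- **That the Trial Steering Committee (TSC) next meets too late to act.** The protocol says "The TSC will meet prior to recruitment commencing and approximately 6-monthly thereafter" and gives no date for the first meeting. Suppose the December 2025 milestone includes wait-list courses. Counting back from 31 December, 6 weeks gives T2 on 19 November, a further 12 weeks gives a course start on 27 August, and that course ends on 8 October. A first meeting on 1 April and a 5-month gap gives 1 September, before that date. Six months from a late-May meeting gives late November, after it. Wait-list courses would still be running into December. The timing is therefore open, and no conclusion is drawn from it.

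**Conclusion.** The point stands in limited form. Before T2, adverse events cannot be recorded for controls at all, or for intervention participants once their course ends. Adverse events as such therefore cannot be compared between arms. Other signs of harm can be, but no summary of deterioration is stated, and the existing escalation and sponsor-alert provisions are not tied to the provider log.

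This is an inexpensive improvement to a pilot's processes, not a flaw that undermines its primary objective of recruitment and retention.

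It rests on three assumptions: that Table 7 is a complete list of what participants are asked; that the appended questionnaires, which were not available to this review, contain no adverse-event question; and that the approximate 8- and 14-week timings hold. If the appended forms already ask such a question in both arms, the asymmetry largely falls away and only the handling of the log remains.

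**What to change.** 1. Add one identical question to the T1 and T2 questionnaires in both arms, on any new or worse health problem or injury since the last questionnaire. Report the answers descriptively by arm. Check it against the service-use questionnaire so that nothing is asked twice.
2. Using scores already collected, report by arm the number with PHQ-9 of 20 or more, or GAD-7 of 15 or more, at T1 and at T2. Give the T0 count alongside, because T0 is collected separately from screening. This is a descriptive count and sets no rule for managing participants.
3. Have each provider's log returned to the trial manager after every course. Reconcile The Intervention, Assessment and management of risk, and Ethical and regulatory considerations with the sponsor-alert undertaking in Role of Trial Sponsor and Funder.

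The cost is one question at two time points, one descriptive table and one form transfer per course, with no new visits. The downsides are a slightly longer questionnaire and self-report by participants who know their allocation, so the by-arm figures should be read as descriptive only.

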# Control Arm

The control arm will continue to receive usual care. To maintain engagement, they will receive a monthly newsletter via email, accessible through our project website. This newsletter will provide updates on the study's progress, recruitment, activities, and related research, helping participants feel connected to the project. For those who prefer a physical copy, a hard copy can be mailed upon request.

At the end of the study, following the collection of outcome measures at T2, they will be offered the opportunity to participate in nature-based activities at the partner sites. Questionnaires and the focus group (see Table 7 and Table 8) will explore the type and nature of any nature-based activity undertaken by the control arm during the waiting period to establish the potential for contamination.

#### Nature-based Providers

Through learning from the feasibility stage, we better understand the challenges of provider participation. Initial workshops led by the research team will be used to support the groups to map their planned activities to the handbook mechanisms, ensure appropriate staff training and staff are in place, and provide details on the research being undertaken. Capacity issues mean that the providers may not be able to deliver more than one course at a time, and that there may be staff turnover, requiring additional input from the research team to ensure new members understand the expectations of the research project. We have allowed eight months for the providers to run up to three six-week courses with approximately 27 participants in series. The viability of this will be assessed in order to inform the full trial in the future.

The meaningful and committed involvement of nature-based providers throughout the project represents significant investment of time and can affect capacity for their day-to-day activities. Therefore, they will be supported by an initial engagement payment which will enable them to participate in training, delivery refinement workshops, administration associated with recruitment and so on.

# Main Objectives

#### Primary objective

• Establishing recruitment (percentage of those screening who participate) and retention rates of participants in intervention and control arms.

#### Secondary objectives

- Intervention arm -attendance at >=67% of sessions (4/6 of the weekly sessions, or twothirds of the intervention)
- Completeness of key outcome measures (PHQ9, GAD7, SWEMWEBS, ONS4, Three-Item Loneliness Scale, health service use questionnaire) at each time-point.
- Estimate the potential effectiveness of the intervention on the outcome measures
- Estimate standard deviations for continuous outcomes
- Intervention costs
- Participant health service use.

# **Data Management**

# **Quantitative Data**

Data will be recorded on the number of participants that are screened for participation and recruited to the pilot trial, further to their attendance of intervention participants at their NBSP intervention course, retention through the trial, and completion of the questionnaire data. Data on participant characteristics (age, gender, education level and postcode) will be collected at baseline. In addition, we will administer the five mental health and wellbeing measures, and the health service use questionnaire (see Appendix).

# Sample size and Power Calculations

As this is a pilot trial a formal sample size calculation for evaluating the impact of the intervention on the outcomes is not appropriate. This pilot RCT will enable us to identify the most appropriate primary outcome (through assessing completeness of data provided, score variability, and participant feedback on completing the questionnaire) and sample size for a future full trial. Based on published recommendations for pilot RCT size of 70 (35 per arm) (Tearle et al 2014) we will aim to recruit 84 participants, allowing for 20% drop out up to T1. Each site will aim to run up to three courses, each accommodating 7–10 participants. The minimum required number of participants per course is four. A total of eight groups with at least four participants each provides sufficient sample size to estimate a dropout rate of 15%, with a 95% confidence interval ranging from 8% to 24%.

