# Recruitment and Participant Identification

We aim to recruit 84 participants (42 in each arm) across three nature-based providers: the Wildfowl and Wetlands Trust, the Eden Project, and the Sensory Trust. These participants will be adults (≥18 years old) with mild-to-moderate depression and/or anxiety, defined by scores of 10-19 on Patient Health Questionnaire (PHQ-9) and/or 5-14 on Generalised Anxiety Disorder assessment (GAD-7).

We will use multiple approaches to reflect the plurality of typical access routes, maximise participant numbers and aim to recruit a diverse population into the study. We will recruit via:

- GP practices in each area
- local link workers/ community connectors
- social media (e.g. local Facebook advertisements, nature-based provider accounts and pages)
- flyers in local community venues, MH support groups

In our single-arm feasibility study, we used both GPs and direct recruitment through social media (local Facebook adverts, nature-based provider routes). While initially recruitment through GPs was slow, reflecting winter workload and staff challenges, we recruited 55% of participants through this route in the feasibility study. Each of the three sites will have three local GPs to support recruitment.

GPs and link workers will receive initial information about the research project through an online seminar. They will identify potential participants and direct them to our project website - https://greengage-research.org - to learn more about the study and sign-up if interested. Those recruited via social media or flyers in local community venues will also be directed to our project website.

The GREENGAGE project website will contain further information about the research, detailing our team, the purpose of the trial, our nature-based provider partners, and what to expect from their participation. The project website will also specify the eligibility criteria and will contain the full participant information sheet in addition to the summary version. Interested users will be prompted to provide consent and will complete the screening questionnaires (see Appendix 1), to ensure that they meet the inclusion criteria. Potential participants will be provided with a mobile telephone number to contact a member of the research team ([name]) if they have further questions about the study or need support completing the questionnaires during working hours.

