# Randomisation and Blinding/Allocation Concealment

The randomisation process will be set up and tested by the trial statistician. Participants will be randomly allocated (using computer generated random numbers) to the intervention or control group, in a 1:1 ratio stratified by location. The aim is to recruit 28 participants at each of the three locations. Within each location, participants will be randomised in two batches of 14, with seven participants allocated to each trial arm per batch. The seven participants in the intervention arm of a given batch will form the group within which they undertake the intervention. As part of this pilot RCT, one key objective is to assess the speed of recruitment. The maximum time we are willing to wait to recruit 14 participants per batch will be reviewed and discussed in team meetings. Currently, it has been decided that a batch will proceed with no fewer than twelve participants (assuming two could drop out, leaving four in an intervention group). However, the specific time frame for reaching this minimum threshold has yet to be determined.

For each batch, the trial manager will provide the statistician with a list of unique, non-identifying participant numbers to maintain allocation concealment. The statistician will then match these numbers to the pre-generated allocation sequence and relay the assigned allocations back to the trial manager. The trial statistician and health economist will remain formally blinded to group allocation until the analysis begins.

Other members of the research team will not be formally blinded, as they may need to access participant data or may inadvertently learn group allocations. For example, green providers may report participant engagement using names (since they lack access to participant identifiers), such as noting if a participant spends intervention sessions on their phone rather than engaging in activities. Additionally, if participants contact the research team to enquire about their group allocation, their names will be recognised alongside their assigned group.

To maintain confidentiality, names, contact details, and participant identifiers will be stored separately and held by the trial manager. Access to these details will be granted only when necessary, such as in cases where a participant poses a risk to themselves or others and needs to be withdrawn from the trial.

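### Recruiting 84 does not allow for 20% dropout from a pilot size of 70: about 67 would remain, and 84 covers only about 16.7% loss

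*Protocol*

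**What the plan says.** The protocol, under Sample size and Power Calculations, declines a power calculation, saying that "a formal sample size calculation for evaluating the impact of the intervention on the outcomes is not appropriate". It justifies the size of the trial by reference to the literature instead: "Based on published recommendations for pilot RCT size of 70 (35 per arm"). The same sentence goes on to the recruitment target: "we will aim to recruit 84 participants, allowing for 20% drop out up to T1".

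The target of 84 appears again in the Trial Summary, in the Methods overview and under Recruitment and Participant Identification, where it reads "We aim to recruit 84 participants (42 in each arm) across three nature-based providers". Under Randomisation and Blinding/Allocation Concealment, allocation is "in a 1:1 ratio stratified by location", and the same total is built up from the delivery structure: "Within each location, participants will be randomised in two batches of 14, with seven participants allocated to each trial arm per batch". With three locations that gives 3 x 2 x 14 = 84.

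**The concern.** Moving from 70 to 84 by way of a dropout allowance makes sense only if 70 is the number wanted with data after dropout. Read that way, the sentence claims that losing a fifth of 84 still leaves 70, and it does not.

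The figure matters because the reference to 70 is the main justification for the overall number recruited. Estimating standard deviations for the definitive trial is a stated objective, and those estimates rest on the participants who provide follow-up data. A reader of the protocol would take 84 to be protected against 20% loss.

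**Working it through.** **Inputs**, all from the protocol:
- Size wanted with data: 70, or 35 per arm (Sample size and Power Calculations).
- Dropout allowance: 20%, up to T1 (same section).
- Recruitment target: 84, or 42 per arm (same section; Recruitment and Participant Identification).
- Allocation: 1:1 (Randomisation and Blinding/Allocation Concealment).

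**Step 1. Try to reproduce 84.** To keep n after a loss proportion d, recruit N = n/(1 - d).
- Total: 70/(1 - 0.20) = 87.5, rounded up to 88.
- Per arm: 35/(1 - 0.20) = 43.75, rounded up to 44.

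This does not give 84. Multiplying by 1 + d does, exactly:
- Total: 70 x 1.20 = 84.
- Per arm: 35 x 1.20 = 42.

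Multiplying adds 20% of the smaller number (14), whereas the loss is 20% of the larger one (84 x 0.20 = 16.8).

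**Step 2. What 84 leaves at 20% loss.**
- Total: 84 x 0.80 = 67.2, about 67. The shortfall is 70 - 67.2 = 2.8, about 3 participants.
- Per arm: 42 x 0.80 = 33.6, so 33 to 34. The shortfall is 35 - 33.6 = 1.4.

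**Step 3. The loss that 84 can absorb.** Setting 84 x (1 - d) = 70 gives d = 1 - 70/84 = 0.167, or 16.7%.

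**Step 4. Effect on precision.** The approximate relative standard error of a standard deviation pooled over two arms is 1/sqrt(2(n - 2)).
- n = 70: 1/sqrt(136) = 8.6%.
- n = 67: 1/sqrt(130) = 8.8%.

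The difference is about 0.2 percentage points.

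**The case against.** The best defence has three parts. First, the protocol calls 70 a recommended size, not a required one, and does not say outright whether it is counted before or after dropout. That is fair as to the word: 70 is a recommendation. But an allowance for dropout added to 70 has no purpose unless 70 is the number to be retained, and no other section offers another reading. Second, 84 may come from the batch structure (3 x 2 x 14) and not from a slip in inflation. That is possible. The exact match with 70 x 1.2 is suggestive, but no formula is shown, so the origin cannot be settled. The sentence is wrong under either origin. Third, the effect is very small. This stands. The primary objective concerns recruitment and retention, and retention is measured on those randomised, so the shortfall does not touch it.

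A reader might also infer three further faults that the protocol does not support:
- **The time point of the allowance is unclear, or should be T2.** The sentence says T1 in terms. No dropout rate to T2 is given, so a larger shortfall there is plausible but cannot be quantified, and stopping at T1 is an explicit choice.
- **The 15% dropout rate later in the same section contradicts the 20%.** The 15% illustrates how precisely a dropout rate could be estimated. A more cautious planning allowance beside an illustrative rate is not a conflict.
- **The batch minimum undermines 84.** The protocol says "a batch will proceed with no fewer than twelve participants". If exactly six batches all ran at that floor, 6 x 12 = 72 would be randomised and 72 x 0.80 = 57.6 would remain. But 12 is a floor for going ahead, the aim stays at 28 per location, and the protocol nowhere claims that the floor preserves 70.

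**Conclusion.** The statement is wrong as written. Recruiting 84 does not allow for 20% dropout from 70. It allows for about 16.7%, and at 20% about 67 participants (33 to 34 per arm) would have data at T1. Keeping 70 would take 88 (44 per arm).

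This rests on one assumption, that 70 is the number wanted with data at T1, which is the natural reading of the sentence. The size is about 3 participants, or 2.8/70 = 4% of the target, in a pilot where no hypothesis is tested and the precision of the standard deviations is almost unchanged. It is an error in a stated figure. It is not evidence that the pilot is too small for its purpose.

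**What to change.** Keep 84 and correct the sentence under Sample size and Power Calculations, for example: *84 participants allow for about 16.7% dropout up to T1 (70 with data); at 20% dropout about 67 (33 to 34 per arm) would have data.*

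Raising the target to 88 would also make the statement true, but 88 does not fit six batches of 14 (6 x 14 = 84), and a gain of about 3 participants with data does not justify changing the batch structure. The other sections that give 84 can stay as they are. The cost is one reworded sentence and a slightly less favourable stated allowance, with no change to design, recruitment or budget.
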